3.3 DOSE MODIFICATIONS

All dose modifications must be discussed with the PI. This study will utilize version 4.0 of the NCI Common Terminology Criteria for Adverse Events (CTCAE) (<http://ctep.cancer.gov/reporting/ctc.html>) for toxicity and adverse event reporting. Expected pre-existing or concurrent manifestations of inflammatory pustular dermatoses include fatigue, malaise, pain, pruritus, arthritis, enthesitis, alopecia, pustular and papular skin lesions, hypopigmentation, hyperpigmentation, skin dryness, nail changes, koebnerization at sites of trauma or injections, uveitis, conjunctivitis, rash, hypocalcemia, hypoalbuminemia and leukocytosis. Any of the above symptoms newly presenting after initiation of anakinra must be carefully evaluated for attribution, i.e., new skin rash may be biopsied to determine drug reaction versus pustular dermatosis. See **APPENDIX D: DOSE MODIFICATION FLOW CHART** for Dose Modification Flow Chart.

Adverse event	CTCAE grade/attribution	Protocol Action
Any adverse event (excluding infection, treatment-related malignancy)	Grade 2 >7 days that is probably or definitely related to anakinra.	Hold study drug; *If AE resolves to \leq grade 1 or baseline within 14 days: resume dose at same dose level. ** If AE does not resolve to \leq grade 1 or baseline within 14 days: patient comes off drug.
Any adverse event (excluding infection, treatment-related malignancy)	Same grade 2 >7 days recurs that is probably or definitely related to anakinra.	Hold study drug; *If AE resolves to \leq grade 1 or baseline within 14 days: decrease dose by 1 dose level. **If AE does NOT

Abbreviated Title: Anakinra in pustular dermatoses

Version Date: December 12, 2018

		resolve to \leq grade 1 or baseline within 14 days: patient comes off drug.
Any adverse event (excluding infection, treatment-related malignancy)	Same grade 2 >7 days recurs after dose reduction that is probably or definitely related to anakinra.	Patient comes off drug.
Any adverse event (excluding infection, treatment-related malignancy)	Grade 3 that is probably or definitely related to anakinra.	Hold study drug; *If AE resolves to \leq grade 1 or baseline within 14 days: decrease dose by 1 dose level. **If AE does NOT resolve to \leq grade 1 or baseline within 14 days: patient comes off drug.
Any adverse event (excluding infection, treatment-related malignancy)	Same grade 3 recurs after dose reduction that is probably or definitely related to anakinra.	Patient comes off drug.
Any adverse event (excluding infection, treatment-related malignancy)	Grade 4 that is probably or definitely related to anakinra.	Patient comes off drug.
Infection	Grade 2 that is probably or definitely related to anakinra	Hold study drug until completion of antibiotic course and resolution of infection, then restart at same dose level.
Infection	Grade 2 recurs that is probably or definitely related to anakinra	Hold study drug until completion of antibiotic course and resolution of infection, then decrease dose by 1 dose level.
Infection	Grade 2 recurs after dose reduction that is probably or definitely related to anakinra	Patient comes off drug.
Infection	Grade 3 that is probably or definitely related to anakinra	Patient comes off drug.
Infection	Grade 4	Patient comes off drug.
Treatment-related malignancy	Grade 3	Patient comes off drug.
Treatment-related	Grade 4	Patient comes off drug.

Abbreviated Title: Anakinra in pustular dermatoses

Version Date: December 12, 2018

malignancy		
------------	--	--

Exceptions to the above treatment modifications:

1. Alopecia any grade
2. Grade 2 anorexia
3. Grade 2 fever
4. Grade 2 fatigue
5. Grade 2 flu-like symptoms
6. Grade 2 chills
7. Grade 2 headache
8. Grade 2 hypoalbuminemia
9. Hypocalcemia toxicity grade should be assigned based on the calcium level corrected for degree of hypoalbuminemia according to the following formula: albumin 1 gram/dL: total calcium 0.2 mmol/L. Ionized calcium can also be used to assess toxicity.
10. Grade 2 injection site reaction
11. Grade 2 malaise
12. Grade 2 nausea
13. Grade 2 dry skin
14. Grade 2 skin or soft tissue infection
15. Grade 2 paronychia
16. Basal cell carcinoma or squamous cell carcinoma of the skin

Doses withheld while recovering from an adverse event should not be made up.

3.4 QUALITY OF LIFE TOOLS/QUESTIONNAIRES

The following quality of life instruments will be administered at baseline, week 4, week 8 and week 12:

1. 36-item Short Form Health Survey is a self-administered multi-purpose, short-form health survey with 36 questions yielding an 8-scale profile of functional health and well-being scores as well as psychometrically-based physical and mental health summary measures and a preference-based health utility index. It is a generic measure. This scale has been used for the measurement of general health status quality of life. This questionnaire will be administered at baseline, week 4, week 8, week 12 and week 16. (10-12 minutes) (**APPENDIX E: SHORT FORM 36 (ENGLISH AND SPANISH)**)
2. Dermatology Life Quality Instrument (DLQI) is a 10-item questionnaire which assesses impact of skin disease on life quality. It is a validated questionnaire which has been used in 33 different skin conditions in 32 countries and is available in 55 languages. It is the most frequently used instrument in studies of randomized controlled trials in dermatology. This questionnaire will be administered at baseline, week 4, week 8, week 12 and week 16. (2 minutes) (**APPENDIX F: DERMATOLOGY LIFE QUALITY (ENGLISH AND SPANISH)**)

Abbreviated Title: Anakinra in pustular dermatoses

Version Date: December 12, 2018

[figure not shown]
3. Pruritus Visual Analog Scale is a self-administered psychometric response instrument which measures subjective characteristics or attitudes that cannot be directly measured. It ranges from 0-10. This scale has been used for measurement in a variety of dermatologic settings. This questionnaire will be administered at baseline, week 4, week 8, week 12 and week 16. (1 minute) (**APPENDIX H: PUSTULAR DERMATOSIS CLINICAL ASSESSMENT SCALE**)
4. Skin Pain Visual Analog Scale is a self-administered psychometric response instrument which measures subjective characteristics or attitudes that cannot be directly measured. It ranges from 0-10. This scale has been used for measurement in a variety of dermatologic settings. This questionnaire will be administered at baseline, week 4, week 8, week 12 and week 16. (1 minute) (**APPENDIX H: PUSTULAR DERMATOSIS CLINICAL ASSESSMENT SCALE**)
5. Joint Pain Visual Analog Scale is a self-administered psychometric response instrument which measures subjective characteristics or attitudes that cannot be directly measured. It ranges from 0-10. This scale has been used for measurement in a variety of dermatologic settings. This questionnaire will be administered at baseline, week 4, week 8, week 12 and week 16. (1 minute) (**APPENDIX H: PUSTULAR DERMATOSIS CLINICAL ASSESSMENT SCALE**)
6. Overall Disease Severity Visual Analog Scale is a self-administered psychometric response instrument which measures subjective characteristics or attitudes that cannot be directly measured. It ranges from 0-10. This scale has been used for measurement in a variety of health settings. This questionnaire will be administered at baseline, week 4, week 8, week 12 and week 16. (1 minute) (**APPENDIX H: PUSTULAR DERMATOSIS CLINICAL ASSESSMENT SCALE**)
7. Health Assessment Questionnaire (HAQ) is a self-administered questionnaire which aims to assess health-related quality of life longitudinally based on five patient-centered dimensions: disability, pain, medication effects, costs of care, and mortality. This instrument is used in the calculation of the ACR70. This questionnaire will be administered with each rheumatology evaluation. (5 minutes) (**APPENDIX I: HEALTH ASSESSMENT QUESTIONNAIRE**)

Completed questionnaires will be maintained in the subject's research chart until study analysis is completed.

Abbreviated Title: Anakinra in pustular dermatoses

[figure not shown]
Version Date: December 12, 2018

3.5 STUDY FLOWCHART

Abbreviated Title: Anakinra in pustular dermatoses

Version Date: December 12, 2018

*Denotes procedure/consultation that is to be performed at the discretion of the investigator.

Abbreviated Title: Anakinra in pustular dermatoses

Version Date: December 12, 2018

3.6 STUDY CALENDAR

	Screening ≤8 weeks prior to enrollment	Baseline- up to drug initiation ^a	Weeks 1, 2, 3 (+/- 3 days)	Week 4 (+/- 1 week)	Weeks 5, 6, 7 (+/- 3 days)	Week 8 (+/- 1 week)	Weeks 9, 10, 11 (+/- 3 days)	Week 12 (+/- 1 week): End of Treatm ent	Weeks 13, 14, 15 (+/- 3 days)	Week 16 (+/- 2 weeks): Post Therapy Follow- up ^a
Eligibility	X	X-update		Clinic visit		Clinic visit		Clinic visit		
Consent		X								
H&P	X	X- update		X		X		X		X
NIH Advanced Directives Form ^b		X								
Medication review	X	X- update		X		X		X		X
Dose titration ^c				X		X				
Telephone surveillance			X		X		X		X	
Immunosuppressant drug taper (per MD discretion)					X	X	X	X		
CBC/diff, serum creatinine and urea nitrogen, hepatic panel with alk. phos, serum B- hCG	X	X		X		X		X		X

Abbreviated Title: Anakinra in pustular dermatoses

Version Date: December 12, 2018

	Screening ≤8 weeks prior to enrollment	Baseline- up to drug initiation ^a	Weeks 1, 2, 3 (+/- 3 days)	Week 4 (+/- 1 week)	Weeks 5, 6, 7 (+/- 3 days)	Week 8 (+/- 1 week)	Weeks 9, 10, 11 (+/- 3 days)	Week 12 (+/- 1 week): End of Treatm ent	Weeks 13, 14, 15 (+/- 3 days)	Week 16 (+/- 2 weeks): Post Therapy Follow- up^a
Blood sampling: calcium, phosphorus, albumin, total protein, ESR, hs-CRP, serum c-peptide		X		X		X		X		X
Urine sampling: UA, calcium, phosphorus		X		X		X		X		X
Ferritin, lipid panel, serum insulin, serum glucose		X								
Serum and urine protein electrophoresis, Parathyroid hormone, Serum 25-OH Vitamin D, anti-nuclear antibody, anti-dsDNA antibodies, anti-ENA antibodies, rheumatoid factor, C3, C4, CH50, HLA typing, quantitative serum immunoglobulins, anti-streptolysin O titer		X								
HIV screen and hepatitis screen	X									
Total body photographs		X		X		X		X		X

Abbreviated Title: Anakinra in pustular dermatoses

Version Date: December 12, 2018

	Screening ≤8 weeks prior to enrollment	Baseline- up to drug initiation^a	Weeks 1, 2, 3 (+/- 3 days)	Week 4 (+/- 1 week)	Weeks 5, 6, 7 (+/- 3 days)	Week 8 (+/- 1 week)	Weeks 9, 10, 11 (+/- 3 days)	Week 12 (+/- 1 week): End of Treatm ent	Weeks 13, 14, 15 (+/- 3 days)	Week 16 (+/- 2 weeks): Post Therapy Follow- up^a
Total body surface area involvement measurement		X		X		X		X		X
PGA scoring		X		X		X		X		X
Skin biopsy	X ^g	X ^h						X ^h		
Quantiferon T gold	X ^d									
Chest X-ray if positive Quantiferon TB Gold	X ^d									
Microbiologic culture of pustule confirming noninfectious etiology	X									
FDG-PET CT scan		X						X		
Joint MRI		X						X		
Research blood sampling		X						X		
Rheumatology Consultation including ACR assessment ^e		X		X		X		X		X
Cardiometabolic evaluation including electrocardiogram		X						X		
Ophthalmologic examination		X						X		
Gastrointestinal consultation		X						X		

Abbreviated Title: Anakinra in pustular dermatoses

Version Date: December 12, 2018

	Screening ≤8 weeks prior to enrollment	Baseline- up to drug initiation ^a	Weeks 1, 2, 3 (+/- 3 days)	Week 4 (+/- 1 week)	Weeks 5, 6, 7 (+/- 3 days)	Week 8 (+/- 1 week)	Weeks 9, 10, 11 (+/- 3 days)	Week 12 (+/- 1 week): End of Treatment	Weeks 13, 14, 15 (+/- 3 days)	Week 16 (+/- 2 weeks): Post Therapy Follow- up ^a
QOL/questionnaires ^f		X		X		X		X		X
Daily scoring diary		Start Day 0		X-----X						
AE Monitoring		START	X	X	X	X	X	X	X	X

^a Additional clinical labs may be obtained as indicated at baseline and follow up visits

^b As indicated in section 10.3, all subjects at NIH will be offered the opportunity to complete an NIH advanced directives form. This should be done preferably at baseline but can be done at any time during the study as long as the capacity to do so is retained. The completion of the form is strongly recommended, but is not required.

^c If escalation criteria are met (see Section 3.2)

^d Within 8 weeks of enrollment

^e If the rheumatology consult is done at Week 0, the patient will be seen again at Week 12. If there is evidence of joint disease, patients will be strongly encouraged to have rheumatology consult during all clinic visits (Weeks 0, 4, 8, 12 and 16)

^f QOL/questionnaires (see Section 3.4)

^g Skin biopsy for hematoxylin and eosin staining to confirm diagnosis if prior confirmational biopsy has not been performed

^h Performed at the investigator's discretion for research purposes

3.7 SURGICAL GUIDELINES

Skin biopsies of lesional and nonlesional skin will be taken at baseline and week 12. Skin biopsy procedure will be explained to the patient and informed consent will be obtained. The risks of infection, scarring, nerve damage, pigment change, numbness, recurrence, bleeding, pain, and allergy to anesthesia will be reviewed. Sterile preparation of the proposed biopsy site will be performed. The biopsy site will be locally anesthetized. Size of punch biopsies will be up to 6mm. One punch biopsy will be performed from nonlesional skin, and up to two punch biopsies will be performed from lesional skin. We will place sutures for hemostasis. Petrolatum and bandage will be applied to the wound site and wound care will be reviewed. Written wound care instructions will be given. We will instruct the patient regarding suture removal.

3.8 OPHTHALMOLOGIC PROCEDURES

3.8.1 Ophthalmic Examination with Dilation

Dilation of the pupils will cause temporary glare and blurring of vision. Rarely an allergic reaction or infection secondary to contaminated drops can occur. Dilating drops can also cause a sudden increase of pressure (acute glaucoma) in eyes that are already predisposed to develop this condition. There is little risk of glaucoma being triggered in this way, but if it is, treatment will be available.

3.8.2 Fluorescein Angiography (if clinically indicated)

The participant's skin may turn yellow for several hours. The yellow color will disappear as the kidney filters the dye from the body. Because the dye passes through the kidneys, the urine will turn dark orange for up to 24 hours after the exam. Some participants may be slightly nauseous (upset stomach) during the exam, but their nausea usually lasts only a few seconds. If the dye leaks out of the vein during the injection, some of the skin around the injection site may feel mildly uncomfortable or become yellow. The mild discomfort usually lasts only a few minutes, and the yellow color goes away in a few days.

Sometimes participants have an allergic reaction to the dye, but this rarely happens. Oral antihistamines are usually used to treat this or the antihistamines may be injected if the symptoms are severe. Very rarely, a participant may have a severe allergic reaction that causes respiratory distress and shock ("anaphylaxis"), which can be life-threatening. Trained personnel with drugs or, possibly, surgery would treat this immediately.

3.8.3 Optical Coherence Tomography (OCT)

There is no medical risk from OCT.

3.8.4 Microperimetry

There is no medical risk from microperimetry.

Abbreviated Title: Anakinra in pustular dermatoses

Version Date: December 12, 2018

3.9 CRITERIA FOR REMOVAL FROM PROTOCOL THERAPY AND OFF STUDY CRITERIA

Prior to documenting removal from study, effort must be made to have all subjects complete a safety visit approximately 28 days following the last dose of study therapy.

3.9.1 Criteria for removal from protocol therapy

- Completion of 12-week anakinra therapy
- Noncompliance with protocol procedures
- Pregnancy
- Participant requests to be withdrawn from active therapy
- Non-allergic toxicity or observed allergic reaction to anakinra
- Investigator discretion
- Positive pregnancy test
- Death

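### Section 3.9.1 removes a patient after an allergic reaction to anakinra, but the Section 3.3 table, read on its own, restarts the drug after some of the same reactions

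*Combined protocol and SAP*

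**What the plan says.** Two sections decide when a patient stops anakinra.

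Section 3.9.1 is a bulleted list of criteria for removal from protocol therapy. One bullet reads "Non-allergic toxicity or observed allergic reaction to anakinra". It gives no grade, duration or degree of attribution, and does not refer to Section 3.3.

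Section 3.3 is a table by grade. Its six general rows are headed "Any adverse event (excluding infection, treatment-related malignancy", so only those two hazards have separate rows. For a probably or definitely related event the general rows work as follows:

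- A first Grade 2 event lasting more than 7 days leads to a hold. If it settles in time, the instruction is "grade 1 or baseline within 14 days: resume dose at same dose level".
- A recurrence of that Grade 2 event, or a first Grade 3 event, also leads to a hold. If it settles in time, the instruction is "grade 1 or baseline within 14 days: decrease dose by 1 dose level".
- If any of these does not settle in time, the instruction is "grade 1 or baseline within 14 days: patient comes off drug".
- Recurrence after a dose reduction, or any related Grade 4 event, takes the patient off drug.

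Sixteen exceptions follow the table. They include Grade 2 injection site reaction, but not allergic reaction, hypersensitivity, anaphylaxis, angioedema or urticaria. Section 3.3 does not mention 3.9.1. It refers to a flow chart in Appendix D, of which only the heading is available here.

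**The concern.** For the same patient the two sections can give opposite instructions. A related Grade 3 allergic reaction that clears in ten days is a reason for removal under 3.9.1 and a restart at a lower dose under 3.3.

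The hazard is recognised in the protocol. Section 11.1.2 says that hypersensitivity, including anaphylaxis, angioedema and urticaria, has been reported with anakinra. Exclusion 2.1.2.9 keeps out anyone with known hypersensitivity to a component of the drug. Restarting a patient who has just shown such a reaction fits poorly with that exclusion.

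Anakinra is self-injected. Section 3.1 states clinic supervision for the first dose only, and no visible text requires it for the first dose after a hold. The trial also has a participating site, so the written text should lead both sites to the same action.

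**Working it through.** No plan figure needs reproducing, because the question is whether two rules agree. I took each general row of 3.3, applied it to an allergic reaction judged probably or definitely related, and compared the result with 3.9.1, which removes the patient in every case. Settled means a return to grade 1 or less, or to baseline, within 14 days.

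| 3.3 general row | Settled | Not settled | Outcomes | Restarts |
|---|---|---|---|---|
| 1. First Grade 2, >7 days | Same dose | Off drug | 2 | 1 |
| 2. Same Grade 2 recurs | One level lower | Off drug | 2 | 1 |
| 3. Same Grade 2 recurs after reduction | Off drug | Off drug | 1 | 0 |
| 4. First Grade 3 | One level lower | Off drug | 2 | 1 |
| 5. Same Grade 3 recurs after reduction | Off drug | Off drug | 1 | 0 |
| 6. Grade 4 | Off drug | Off drug | 1 | 0 |

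Rows 3, 5 and 6 stop the drug whether or not the event settles, so each counts as one outcome.

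- Total outcomes: 2 + 2 + 1 + 2 + 1 + 1 = 9.
- Outcomes that restart the drug: 1 + 1 + 1 = 3 (rows 1, 2 and 4).
- Outcomes that take the patient off drug: 9 − 3 = 6. These agree with 3.9.1.

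Restarts along one patient's path, if every episode settles within 14 days:

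- Recurring Grade 2 reaction of more than 7 days: row 1, then row 2, then off at row 3. That is 1 + 1 = 2 restarts.
- Grade 3 reaction: row 4, then off at row 5 ("Same grade 3 recurs after dose reduction that is probably or definitely related to anakinra"). That is 1 restart.
- Under 3.9.1: 0 restarts.

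By the dose levels in Section 3.1.2, one level lower means 300 to 200, 200 to 100, or 100 to 50 mg/day.

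I then looked for text that settles which section governs.

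- **Exceptions in 3.3.** None of the 16 covers allergy.
- **Exclusion 2.1.2.9.** It applies at entry, not on treatment.
- **Section 3.1.** Related serious events of grade 3 or greater require an immediate hold and emergency evaluation. This does not say what happens after the hold, and it does not reach Grade 2 events.
- **Section 3.1.1.** Related toxicity of grade 3 or greater goes to the IRB and the safety monitor for review. No action is fixed for the individual patient.
- **Sections 3.3, 4.1, 7.4.1 and 3.9.1.** Dose changes are discussed with the principal investigator, a new rash is worked up for cause, patients contact the team at once, the team meets weekly, and the investigator may remove a patient. These provide a place to decide but do not state the decision.

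The table already has the structure for a separate rule. For infection, a single event described as "Grade 3 that is probably or definitely related to anakinra" takes the patient off drug. The same grade and attribution in the general rows leads to a restart if the event settles.

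**The case against.** The strongest reply is that a site reads the two sections together. Section 3.9.1 names allergic reaction and 3.3 speaks of adverse events in general; if the specific rule overrides the general one, the answer is removal. That is probably how a careful investigator would act, and 2.1.2.9 points the same way. But the protocol does not state this order of precedence.

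A second reply is that the 3.9.1 bullet cannot be literal. It also lists non-allergic toxicity without a grade, which would cancel every hold-and-resume row in 3.3. The bullet may simply record reasons for coming off therapy. This point stands as a description of loose drafting, but it does not remove the problem. If the bullet is literal, the sections contradict each other. If it is shorthand, the 3.3 restart rule stands for allergic reactions.

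A third reply is that Appendix D may have an allergy branch, and that Section 11.1 refers to the package insert. Neither can be checked here. An allergy branch in Appendix D could show the intent, but the 3.3 table and 3.9.1 would still disagree.

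Two further points are fair. Counting table outcomes does not measure risk, and the count covers only events that have a row in 3.3. Grade 2 reactions of 7 days or less have no row there, while 3.9.1 sets no duration. Harm would also require the principal investigator to agree to a restart despite a named removal criterion.

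**Conclusion.** The concern holds. On the visible text, three of the nine outcomes in the general rows of 3.3 restart anakinra where 3.9.1 calls for removal. One patient could be restarted twice after a recurring Grade 2 reaction, or once after a Grade 3 reaction. The sections agree for "Grade 4 that is probably or definitely related to anakinra", for events that do not settle within 14 days, and for recurrence after dose reduction.

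This is a conflict between two written rules, not a positive instruction to rechallenge after allergy. It assumes that the reaction is graded and attributed under the general rows and that the unseen Appendix D does not settle the matter. The documents give no rate of allergic reactions, so the number of patients affected cannot be estimated. The response-rate estimate, sample size, confidence interval and early stopping rule are unaffected. It should be fixed because it bears on patient safety and the correction is small. Confidence is medium, because Appendix D is not shown and several safeguards make a restart less likely in practice.

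**What to change.** 1. In Section 3.3, add allergic and hypersensitivity reactions to the hazards excluded from the general rows, and give them one row: *allergic or hypersensitivity reaction (for example anaphylaxis, angioedema, urticaria), probably or definitely related to anakinra: off drug, no rechallenge.* State in that row that injection site reactions and rash attributed to the pustular disease do not count.
2. In Section 3.9.1, replace the bullet with: *toxicity requiring discontinuation under Section 3.3, including allergic reaction to anakinra.* This also resolves the ungraded non-allergic half of the bullet.
3. Check Appendix D and align it with both sections.

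The attribution threshold and the two exclusions are proposals that 3.9.1 does not contain. If the sponsor prefers a grade threshold for stopping, it should be stated identically in both sections. A cross-reference in Section 3.1.2 is optional.

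The cost is wording in two sections and a check of one flow chart, with no added visits, tests or patients. The drawback is that an occasional patient with a mild reaction loses therapy, which 3.9.1 already implies.
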